7.3.2 Analyses of Secondary Efficacy Endpoints

The following secondary efficacy endpoints will be analyzed using the same methods as described for the primary efficacy endpoint of TB disease recurrence (see Section 6.3.1).

Methods for comparison of WGS of paired *Mtb* isolates in participants with TB disease recurrence will be described in the statistical analysis plan.

- Rate of TB disease relapse, defined as participants meeting the primary endpoint of TB disease recurrence, AND determined by WGS of the *Mtb* isolate to be the same strain of *Mtb* as in the participant's original isolate from the time of diagnosis
- Rate of TB disease reinfection, defined as participants meeting the primary endpoint of TB disease recurrence, AND determined by WGS of the *Mtb* isolate to be a different strain than in the participant's original isolate from the time of diagnosis

.Analyses of Exploratory Efficacy Endpoints

The following exploratory efficacy endpoints will be analyzed using the same methods as described for the primary efficacy endpoint of TB disease recurrence (see Section 7.3.1):

- Rate of TB disease recurrence (relapse or reinfection), defined as participants meeting the primary endpoint of TB disease recurrence AND participants who started TB treatment without confirmation of *Mtb* by culture of sputum
- Rate of TB disease recurrence (relapse or reinfection), defined as participants meeting the primary endpoint of TB disease recurrence based on confirmation of *Mtb* by Xpert MTB/RIF Ultra or culture of sputum
- Rate of TB disease recurrence (relapse or reinfection), defined as participants meeting the primary endpoint of TB disease recurrence AND participants diagnosed between 30 days after the 1st vaccination and 14 days after the 2nd vaccination, based on confirmation of *Mtb* by culture of sputum

7.4 Immunogenicity and Immunology Analyses

Immunogenicity and immunology analysis will be summarized for all time points as collected and as available. The immunogenicity endpoint analysis will be based on participants in the immunogenicity analysis set (defined in Section 7.1). No imputation for missing data will be performed. Data will be transformed as appropriate prior to analysis.

7.4.1 Intracellular Cytokine Staining (WB ICS) Using Whole Blood

This is a secondary endpoint in the study, see Section 2.1.3.1 and Table 3-2, and it is the primary immunogenicity endpoint. This endpoint will be measured in the immunogenicity cohort (see Table 2-1) at V3= Day 0 and V6= Day 70.

Responses will be measured by flow cytometry (up to 15 parameters) with the whole blood based ICS assay. The variables of interest for assessment of antigen-specific cell-mediated immune response to vaccination will be the percentage of CD4+ and CD8+ T cells that express selected cytokines and phenotypic markers alone or in combination in response to stimulation with peptide pools representing the entire amino acid sequence of the vaccine antigens.

Frequencies of background (unstimulated control) subtracted cytokine responses will be expressed as medians and associated 95% confidence intervals or other descriptive statistics as appropriate will be used to summarize percentage T cell responses. Summaries of T cell responses will be presented by T cell type (CD4+ and CD8+) and by stimulation antigen. Summaries will include immune response at all available pre- and post-vaccination immunology time points, and change from pre-vaccination to post-vaccination time points.

Analytic approaches for these endpoints will be informed by best practice and the most recent advances in vaccinology and systems biology.

7.4.2 Antigen-specific IgG ELISA Assay Using Plasma

This is a secondary endpoint in the study, see Section 2.1.3.1 and Table 3-2, and is the secondary immunogenicity endpoint. This endpoint will be measured in the immunogenicity cohort (see Table 2-1) at V3= Day 0 and V6= Day 70. For remaining participants, it is an exploratory endpoint at V3= Day 0, V6= Day 70 or at suspicion of a diagnosis of recurrent TB at the time of evaluation of TB recurrence. Antigen-specific antibody will be assessed in plasma by enzyme linked immunosorbent assay (ELISA). Summaries will include immune response at all available pre- and post-vaccination immunology time points, and change from pre-vaccination to post-vaccination time points.

7.4.3 RNA Analysis and Blood Subset Counts Supporting RNA Analysis Using Whole Blood

These are exploratory endpoints in the study, see Section 2.1.4.1 and Table 3-2. These endpoints will be measured in all participants at V3= Day 0 and in participants with suspicion of a diagnosis of recurrent TB at the time of evaluation of TB recurrence. Whole blood gene expression profiles will be measured by RNA sequencing and microfluidic qRT-PCR on PAXgene samples in a subset of participants: those who developed TB recurrence and a selected group of controls.

Cellular composition of whole blood leukocytes will be characterized by flow cytometry in order to deconvolve transcriptomic patterns to account for changes in peripheral blood cell numbers.

Transcriptomic signatures of inflammation and gene expression pathways as well as transcriptomic signatures associated with risk of TB recurrence and prediction of adaptive responses will also be investigated.

The determination of absolute blood subset counts will support the RNA analysis.

Analytic approaches for these endpoints will be informed by best practice and the most recent advances in vaccinology and systems biology.

7.4.4 Intracellular Cytokine Staining (ICS) Using PBMCs

This is an exploratory endpoint in the study, see Section 2.1.4.1 and Table 3-2. This endpoint will be measured in all participants at V3= Day 0 and V6= Day 70 and in participants with suspicion of a diagnosis of recurrent TB at the time of evaluation of TB recurrence.

Analysis of cells stimulated with relevant antigens (ESAT-6, Ag85B, Rv2660c, as well as negative and positive controls) will include T, B and other lymphocyte lineages (such as NK and MAIT cells), expression of differentiation and activation markers as well as cell functions (such as cytokine production and cytotoxic potential). Responses will be measured by flow cytometry (up to 28 parameters) using a PBMC based ICS assay.

7.4.5 Exploratory Immunology at TB Recurrence - Control Samples

The exploratory immunology samples to be taken at the time of evaluation of TB recurrence, from participants with a suspected diagnosis of recurrent TB disease will be: PBMC and plasma for ICS and IgG ELISA and whole blood for RNA analysis and Blood subset counts (that support the RNA analysis), see Table 3-2.

For the analysis of these samples, “control samples” from a “control cohort” are needed.

The immunology samples taken at V8= Day 421 from the participants in the immunogenicity cohort (excluding participants with recurrent TB, if any), see Table 2-1, will be these “control samples”. See Table 3.1.

7.4.6 Adverse Events

The primary variable for evaluation of the safety profile will be the number and percentage of adverse events recorded after the first administration of vaccine on Study Day 0. The number of events and number (percentage) of participants with unsolicited adverse events and solicited adverse events will be summarized by MedDRA system organ class and preferred term. Additional summaries will present the number of events and number (percentage) of participants with adverse events by severity and by relationship to investigational product; Listings will be provided for participants with serious adverse events.

7.4.7 Injection Site Reactions

The number (percentage) of participants recording injection site reactions (redness, swelling and tenderness/pain) and axillary lymphadenopathy will be summarized by treatment group and post-vaccination time point. In addition, measurements (recorded in mm) of redness and swelling will be summarized as continuous parameters by treatment group.

7.4.8 Clinical Laboratory and Vital Sign Parameters

For each clinical laboratory and vital sign parameter pre-specified in the protocol, summary statistics for continuous parameters will be presented by treatment group for all pre- and post-

vaccination assessments and for change from pre-vaccination to post-vaccination assessments.

The number (percentage) of participants with post-vaccination clinical laboratory values or vital sign values recorded as newly abnormal following study vaccination will be tabulated at each post-vaccination time point and overall. Clinical laboratory and vital sign abnormalities will also be reported as adverse events and included in the summaries of adverse events.

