4.1 Statistical Considerations

Baseline is defined as the last assessment with available data prior to the first vaccination. No statistical tests comparing treatment groups at baseline will be performed.

Categorical data will be summarised by treatment group, using number and percentages of participants. Continuous data will be presented using the number of participants (N), mean, standard deviation (SD), median, lower quartile, upper quartile, minimum and maximum. Both the absolute values and the change from baseline will be presented, if applicable. For calculation of percentages the denominator will be the number of participants in the analysis set, unless otherwise specified.

Descriptive statistics for all endpoints will be presented by treatment group and Visit (if applicable) using observed cases, i.e., no imputation of missing data will be performed. Missing data for time to event endpoints is handled using censoring.

All presentations will at least be by treatment group.

For summaries presented by visit, scheduled time will be used, and trial visits will be labeled as below:

Visit	Label
3	Visit 3 (Day 0) - Baseline
4	Visit 4 (Day 14)
5	Visit 5 (Day 56)
6	Visit 6 (Day 70)
7	Visit 7 (Day 238)
8	Visit 8 (Day 421)

The following labels will be used in tables, figures, and listings:

Treatment	Label
H56:IC31: 5 µg H56/500 nmol IC31	H56:IC31
Placebo	Placebo

All will be presented in UK English.

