7.2.2 Other Safety Assessments

Injection site reactions

Injection site reactions (*redness, swelling, tenderness/pain, and other* as judged by the investigator) and axillary lymphadenopathy, defined as Lowest Level Term Lymphadenopathy axillary, on the same day as a vaccination as well as all injection site reactions after latest vaccination will be presented as follows:

- The number and percentage of participants as well as number of events will be summarised by treatment group and by vaccination (starting after 1st and after 2nd vaccination).
- The maximum size of the redness and swelling on the same day as a vaccination and in total within 7 days after latest vaccination will be summarised by treatment group and by vaccination.
- Injection site reactions will be listed including type and maximum diameter in mm and onset relative to the two vaccinations.

Temperature reactions (pyrexia)

Temperature reactions are events with PT *Pyrexia*. The maximum temperature could be recorded in the CRF. The maximum temperatures will be summarised by treatment group and vaccination (1st and 2nd). A listing will be made for all systemic reactions including pyrexia with maximum temperature if available.

Vital Signs

Vital signs (systolic and diastolic blood pressure, pulse, and axillary temperature) will be measured at each visit from 2nd screening visit (Visit 2) to Visit 6 (Day 70), and at ET visit. At Visits 3 and 5, the measurements are taken both pre-vaccination and one-hour post-vaccination.

Vital signs will be summarised by visit, including change from pre-vaccination to post-vaccination within Visit 3 and 5, respectively. For each visit it will be flagged whether there are any abnormal clinically significant vital signs. All information will be listed.

Height, Weight, and BMI

Weight is measured at all onsite visits from 1st screening visit (Visit 1) and onwards. Weight will be summarised by treatment and visit, including change from baseline, (Visit 3, Day 0) to subsequent visits. Height is measured at 1st screening visit (Visit 1) and BMI will be calculated for that visit. Height and BMI will be summarised by treatment, see section 4.3. All information will be listed. Furthermore, a box plot will present weight by visit and treatment.

Physical Examination

A complete physical examination is performed at 2nd screening visit (Visit 2). Symptom directed physical examination is performed at the two vaccination visits, Visit 3 and Visit 5. Each body system

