7.2.3 Laboratory Safety Data

Laboratory safety (haematology, biochemistry, and urine analysis parameters) are measured at 2nd screening visit (Visit 2) for all participants, and at Visit 4 (day 14), Visit 6 (day 70) and at ET visit for participants in the safety cohort. Laboratory safety will also be measured at the ET visit if the visit occurs within 14 days after investigational product administration. Additional laboratory tests may be performed if deemed necessary by the investigator for evaluation of an AE.

The following safety laboratory parameters are measured and will be presented using SI units:

- Serum chemistry: AST ($\mu\text{Kat/L}$), ALT ($\mu\text{Kat/L}$), ALP ($\mu\text{Kat/L}$), GGT ($\mu\text{Kat/L}$), total bilirubin ($\mu\text{mol/L}$), creatinine ($\mu\text{mol/L}$).
- Hematology: haemoglobin (g/L), haematocrit (L/L), leukocytes ($10^9/\text{L}$), lymphocytes ($10^9/\text{L}$), monocytes ($10^9/\text{L}$), neutrophils ($10^9/\text{L}$), basophils ($10^9/\text{L}$), eosinophils ($10^9/\text{L}$), and platelets ($10^9/\text{L}$).
- Urine analysis: urine protein, glucose, leukocytes, and erythrocytes (microscopy if positive by dipstick).

Laboratory safety biochemistry and haematology will be presented by visit and treatment using summary tables and boxplots. Urinalysis will be summarised by visit and treatment using the categories as collected in the eCRF.

All safety laboratory data will be listed by participant, including unscheduled measurements. Values outside normal ranges will be flagged and presented in a separate listing including normal ranges.

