8.3 Other derivations

Duration of AEs

Duration of an AE in days will be calculated as:

$$\text{Date}_{\text{AE end}} - \text{Date}_{\text{AE start}} + 1$$

The calculation will be based on AE dates after handling of partial dates. Duration will not be calculated for ongoing AEs.

Time to event

Time to event (or censoring) in days will be calculated as

$$\text{Date}_{\text{end-timepoint}} - \text{Date}_{\text{start-timepoint}} + 1$$

9 Deviations from protocol

The following deviations in the statistical analyses compared to the protocol are made:

- The protocol section 6.1 states that the per-protocol [PP] analysis set will consist of all participants who received both doses of H56:IC31 or placebo within the specified dose intervals, who entered the evaluation period for efficacy 14 days after receipt of the second dose of H56:IC31 or placebo with no HIV seroconversion, and who had no major protocol deviations (to be defined in the statistical analysis plan). Regarding major protocol deviations, the definition is updated to *who had no major protocol deviation of clinical or statistical significance*.
- The protocol section 7.3.1 states that supportive robustness and consistency analysis will be performed using the PP and ITT populations for the primary endpoint. Since
 - the only difference between the mITT and the ITT population is that the mITT will include all randomised participants except those with TB disease recurrence before Visit 6, Day 70
 - the primary endpoint only include TBs diagnosed by confirmation of *Mtb* by culture of sputum, during the period starting 14 days after the 2nd vaccination (Day 70, Visit 6) then are the mITT and ITT analyses exactly identical, why the ITT analyses of the primary endpoint from day 70 will be replaced by analyses from day 0.
- The protocol section 7.3.1 states that summaries of median time to initial diagnosis of TB disease recurrence will be presented by treatment group and trial site. Due to the expected low number of recurrent TB diseases, it will not be possible to estimate the median time to initial diagnosis and this is therefore not included in the SAP. The endpoint contains censored events and a non-parametric summary of time to TB disease recurrence is not appropriate.

10 Software

All statistical calculations described in this SAP will be done by using SAS, release 9.4 or later (SAS Institute, Cary, NC, USA).

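### The SAP omits the protocol's table of newly abnormal laboratory and vital sign values and does not declare the omission in its section 9

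*Protocol*

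**What the plan says.** Protocol 7.4.8 makes three commitments for laboratory and vital sign parameters. The first is continuous summaries by treatment group, including change after vaccination. The second is a count and percentage of participants whose values are "recorded as newly abnormal following study vaccination will be tabulated at each post-vaccination time point and overall". The third is that abnormalities will, in addition, be handled as adverse events and enter those summaries.

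SAP 7.2.3 covers the laboratory data: "Laboratory safety biochemistry and haematology will be presented by visit and treatment using summary tables and boxplots". Urinalysis is summarised by visit and arm in the categories collected. For abnormal values the text is: "Values outside normal ranges will be flagged and presented in a separate listing including normal ranges".

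SAP 7.2.2 covers vital signs: "Vital signs will be summarised by visit, including change from pre-vaccination to post-vaccination within Visit 3 and 5, respectively". For abnormality it adds: "For each visit it will be flagged whether there are any abnormal clinically significant vital signs. All information will be listed".

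SAP section 1 says that departures from the protocol's analyses are highlighted in section 9. That section opens with "The following deviations in the statistical analyses compared to the protocol are made" and gives three items: the per-protocol definition, the ITT analysis from day 0, and the median time to recurrence.

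**The concern.** A continuous summary describes the whole distribution. It does not say how many participants moved from normal before vaccination to abnormal after it. A mean or median hardly moves when a few participants shift, and a maximum shows one value but not how many lie near it. A listing contains the cases but gives no rate by arm. The table in Protocol 7.4.8 was meant to supply that rate.

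Scheduled post-dose laboratory tests are confined to the safety cohort, the first 150 randomised. SAP 7.3 states that the two reviews of that cohort were blinded and compared no arms, so the final report is where these data are to be compared. Protocol 1.5 gives some reason to look at individual shifts: a related vaccine with the same adjuvant had one participant with raised AST/ALT and one withdrawn for rising eosinophils. Both were reported as adverse events, so they show that such shifts occur, not that the adverse event tables would miss them.

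The omission is also undeclared. A reader who relies on section 9 would conclude that the laboratory and vital sign analyses follow the protocol in full.

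**Working it through.** No formula applies to the main point; it is a comparison of texts.

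**1. Commitment against delivery**

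| Protocol 7.4.8 | SAP text | Table shells |
|---|---|---|
| Continuous summaries by arm | Kept (7.2.2, 7.2.3) | Kept (14.3.3.1–14.3.3.4, 14.3.5.1–14.3.5.16) |
| Change after vaccination | Kept: SAP 4.1 calls for change from baseline where applicable; 7.2.2 adds change within Visits 3 and 5 | Laboratory shell 14.3.5.1 has no change rows; vital sign shells have them only within Visits 3 and 5, not for Visits 4 and 6 |
| n (%) newly abnormal, per time point and overall | Absent | Absent |
| Abnormalities also in the adverse event summaries | By-arm adverse event tables (7.2.1) | 14.3.1.x |

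**2. Shell count.** Vital signs and weight 6 (14.3.3.1–14.3.3.6), TB symptoms 1 (14.3.4), laboratory 20 (14.3.5.1–14.3.5.20): 6 + 1 + 20 = 27. Shells that count newly abnormal participants: 0.

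**3. Where abnormality flags appear.** Only in listings: 16.2.8.1 (a clinical significance flag per visit), 16.2.9.1 and 16.2.9.2 (reference range indicator and clinical significance), 16.2.9.3 and 16.2.9.4. The separate listing promised in SAP 7.2.3 is of values outside normal ranges, whereas 16.2.9.4 is titled for clinically significant values only.

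**4. Is urinalysis a substitute?** Shells 14.3.5.17–14.3.5.20 count categories by visit and arm. They do not compare with baseline and have no overall row, so they do not give the newly abnormal count even for urinalysis.

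**5. Are the adverse event tables a substitute?** Protocol 7.4.8 makes them an addition to the table. Protocol 5.2 limits laboratory and vital sign adverse events to changes that the investigator considers clinically significant, and Protocol 3.6.3.2 makes the reporting discretionary. A new out-of-range value not reported as an event is therefore counted in no by-arm table.

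**6. Is the count by arm?** The Protocol 7.4.8 sentence on new abnormalities does not itself name treatment group. The reading rests on the preceding paragraph, which does, and on SAP 4.1: "All presentations will at least be by treatment group".

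**7. Declaration.** Items in SAP section 9: 3. Items on laboratory or vital sign analyses: 0.

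**8. Size of the groups** (planned numbers)
- Laboratory: 150 / 2 = 75 per arm; one participant is 1/75 = 1.3%. Early termination visits within 14 days of a dose may add a few.
- Vital signs: taken from all participants through Visit 6, 900 / 2 = 450 per arm; one participant is 1/450 = 0.2%.

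**The case against.** The strongest reply is that little is lost. Clinically significant abnormalities should be reported as adverse events. Visits 4 and 6 fall 14 days after each dose, so those events should appear by arm in 14.3.1.2 and 14.3.1.20, and by severity and causality in 14.3.1.7 and 14.3.1.8. The continuous shells show quartiles and extremes. Protocol section 7 calls itself an outline, and Protocol 7.6.3 allows the SAP to modify the analyses. SAP 7.1 classes vital signs and laboratory parameters as additional assessments.

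Much of this stands, and it rules out four stronger readings that a reader might infer:

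- That the SAP offers nothing but listings for laboratory and vital sign data. By-arm continuous summaries and urinalysis counts remain.
- That change from baseline was dropped. SAP 4.1 keeps it; only the shells lack the rows.
- That an imbalance in abnormal values would appear in no planned table. Abnormalities reported as adverse events would appear by arm.
- That a key secondary endpoint goes unanalysed. Those endpoints are solicited and other adverse events within 14 days and serious adverse events.

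Two things remain. Reporting as an adverse event is discretionary, so the adverse event tables do not replace the count. And Protocol 7.6.3 expects a modification to be included in the SAP; silence does not do that.

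**Conclusion.** The point holds in a limited form. A pre-specified descriptive safety table is missing from the SAP text and all 27 relevant shells, and section 9 does not declare it. What is lost is the by-arm count of new out-of-range chemistry, haematology and vital sign values that are not reported as adverse events. How many there will be cannot be derived from the documents. The resolution would be 1.3% of an arm per participant for laboratory tests and 0.2% for vital signs.

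The conclusion rests on reading the promised table as by arm and on planned cohort sizes. Neither document defines newly abnormal, so a definition is needed in any case. The table supports the key secondary safety objective without being one of its endpoints. It should be restored, but nothing in the primary or key secondary analyses depends on it.

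**What to change.** Add to SAP 7.2.2 and 7.2.3, and to the shells, by-arm tables of the number and percentage of newly abnormal participants, per post-vaccination visit and overall. Specify:

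- **Definition:** not abnormal at baseline, and outside the reference range or flagged abnormal after vaccination. The vital sign flag is set per visit, and Visit 3 holds both a pre-dose and a post-dose reading, so the SAP must say which assessment serves as baseline.
- **Denominator:** participants with a baseline and a post-vaccination value. For laboratory tests this is essentially the safety cohort, about 75 per arm, not the whole safety analysis set. For vital signs it is all vaccinated participants, about 450 per arm.
- **Change from baseline:** add the rows to laboratory shell 14.3.5.1, and to the vital sign shells for Visits 4 and 6, as SAP 4.1 already requires.

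If the table was left out on purpose, section 9 should say so and give the reason.

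The cost is a few more descriptive tables. Listing shell 16.2.9.1 already carries the reference range indicator they need for laboratory values. There is no effect on testing or multiplicity.
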